Patients that experience a lenalidomide-related hematologic DLT may continue on therapy if the event resolves, the investigator considers it in the best interest of the patient to continue and the patient qualifies for initiation of the next cycle with standard of care lenalidomide dose reduction. However, the DLT will count towards establishment of maximally tolerated dose (MTD). A cohort will be expanded if 1 of 3 pts experiences a DLT. If 2 of 6 pts on a cohort experience a DLT, then MTD will be determined as the dose level immediately below that in which 2 of 6 pts experience a DLT. The Phase II portion of the trial will commence upon completion of the Phase I portion. In the event that a MTD is not established, safety and tolerability data collected in the Phase I portion of the study will guide decisions on dosing of CT-011 in the phase II trial.

The maximum tolerated dose level (MTD) combination is defined as the dose level at which no more than one of six patients experiences a DLT as defined above. Any dose level that has two or more DLTs reported is considered to exceed the MTD and not be a tolerable dose level. Dose escalation will be determined based on the occurrence of DLTs observed in the first cycle of therapy. For the purposes of dose determination, DLTs will be counted by patient, i.e., a patient who experiences more than one DLT will be counted only once.

Discontinuation of treatment due to disease progression will not constitute a DLT. In the phase I portion of this trial, if a patient goes off treatment before completing cycle one for reasons other than toxicity or DLT, they will be replaced at that dose level to fully evaluate the tolerability of this regimen at that dose level.

After 4 cycles of therapy or earlier if clinically indicated, response determination will be assessed by the IMWG criteria. At the end of Cycle 4, if a subject has responded (complete or partial response) or has stable disease, dosing with CT-011 and lenalidomide will continue for a minimum of 8 additional cycles or until withdrawal.

If disease progression is observed at the end of Cycle 4 evaluation, all study therapy will be discontinued. Confirmation of progression of disease will be done according to the IMWG criteria.

Following the 30-day post-treatment follow-up assessment, additional evaluations will occur once per month (unless subject discontinued due to progression) until

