the earliest of the following events: disease progression, the time of initiation of new therapy, death or study completion.

Study completion is defined as 30 days after the last subject remaining on study medication discontinues study medication.

For the Phase II portion

Upon completion of the cohorts in phase I, the phase II portion of the study will commence utilizing the planned target doses (or MTDs determined) with CT-011 in combination with lenalidomide and dexamethasone

During the phase II portion of this trial, we will not evaluate patients for DLTs as was done in the phase I portion; however, we will use the DLT criteria to identify potential toxicity and tolerability concerns occurring at any cycle to initiate further evaluation to ensure safety of patients. An independent Data Monitoring Committee will continue oversight of this trial.

Treatment will continue until Progression of disease, death, unacceptable toxicity or patient or treating physician decision to discontinue therapy.

Dosing Regimen

Dosing cohorts for the phase I study: We will conduct a standard 3+3 design over 4 dose levels of 1.5, 3, 3, and 6 mg/kg of CT-011 given intravenously every 4 weeks (28 days) on day 3, and lenalidomide given at 15, 15, 25, and 25 mg orally daily on days 1-21 of a 28-day cycle. The study drug CT-011 and lenalidomide can move independently of one another as described in the Table below. Dexamethasone 40 mg orally weekly may be added if only stable disease after 3 cycles according to the IMWG response criteria (section 13-0). Dexamethasone can be reduced to 20 mg based on tolerability or if patient is 70 years or older.

A minimum of 3 patients to a cohort with at least one week break between cohorts.

	CT-011- mg/kg day 3
Cohort -1	1.5
Cohort -2	1.5
Cohort 1	1.5
Cohort 2	3
Cohort 3	3
Cohort 4	6

	Lenalidomide- mg Days 1-21
Cohort -1	10
Cohort -2	5
Cohort 1	15
Cohort 2	15
Cohort 3	25
Cohort 4	25

If a DLT occurs in 2 or more patients during the first cycle, we will consider this

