dose level to exceed the MTD and therefore be deemed intolerable for this patient population. If a DLT occurs in 1 of 3 patients during this time, an additional 3 patients will be enrolled and evaluated for DLT before dose escalation can proceed. If no other patient in the cohort has a DLT, escalation to the next cohort may proceed 1 week later from the last included patient on the current cohort. If a second patient in a cohort has a DLT, MTD determination will then be conducted by one of the following schemes:

- If ≥ 2 of 3 patients in cohort 1 exhibit a DLT at the dose of 1.5 mg/kg CT-011 in combination with lenalidomide 15 mg, 3 more patients will be enrolled at a de-escalated dose level cohort. This de-escalation cohort (Cohort -1) will use the same dose of CT-011 (1.5 mg/kg) in combination with 10 mg lenalidomide. If no further DLTs are observed, we will consider dose escalation of the CT-011 with this lower dose of lenalidomide such that the dose escalation of CT-011 to 3 mg/kg with lenalidomide 10 mg will proceed in the next cohort. However, if ≥ 2 patients experience DLT with CT-011 1.5 mg/kg and lenalidomide 10 mg, then we will further de-escalate lenalidomide to 5 mg and enroll 3 more patients on CT-011 1.5 mg/kg combined with lenalidomide 5 mg. The same criteria for MTD will be used for these de-escalation dose level cohorts.
- If ≥ 2 patients in cohort 2 exhibit a DLT at the dose of 3 mg/kg CT-011 in combination with lenalidomide 15 mg, we will explore tolerability of an intermediate dose level of lenalidomide, where 3 patients will be enrolled and treated with 3 mg/kg of CT-011 in combination with 10 mg lenalidomide. The dose escalation of CT-011 to 6 mg/kg with lenalidomide 10 mg will proceed in the next cohort if no more than one DLT is observed in the 3 mg/kg CT-011+10mg lenalidomide cohort.
- If ≥ 2 patients in cohort 3 exhibit a DLT at the dose of 3 mg/kg CT-011 in combination with lenalidomide 25 mg, 3 more patients will be enrolled at the 3 mg dose of CT-011 in combination with 15 mg lenalidomide. If there is < 1 DLT with CT011 3mg/kg and lenalidomide 15 mg, this will be defined as the MTD. If there are 2 or more DLT, then 3 additional patients will be enrolled at the CT-011 3mg/kg and lenalidomide 10 mg, which will become the MTD.

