4 STUDY DESIGN AND DURATION

4.1 Study Design

This is a non-randomized open-label phase I/II study for patients with relapsed and refractory multiple myeloma. For the phase I part, we will conduct a standard 3+3 design over 4 main dose levels cohorts evaluating 1.5, 3, 3, and 6 mg/kg of CT-011 given intravenously every 4 weeks (every 28 days) on day 3, and lenalidomide given at 15, 15, 25, and 25 mg orally daily on days 1-21 of a 28-day cycle, to determine the maximum tolerated dose. The phase II will commence once the MTD is determined, and this dose level combination for CT-011 and lenalidomide will be used for the phase II portion of this trial. Patients will be assessed for response at the end of cycle 4 or sooner if necessary according to the IMWG response criteria.

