4.2 Definition of Dose Limiting Toxicity

For the phase I portion, patients will be monitored for safety by assessing toxicities as graded by the NCI CTCAE v4.0. The maximum tolerated dose (MTD) or dose limiting toxicity (DLT) will be defined as one or more of the following toxicities considered to be at least possibly related to one of the study drugs during Cycle 1:

- Grade 3 or greater non-hematologic toxicity with the exception of Grade 3 nausea, vomiting and diarrhea that responds to supportive therapy.
- Grade 4 thrombocytopenia, or grade 3 thrombocytopenia with bleeding, or any requirement for platelets transfusion

- Grade 4 neutropenia persisting for more than 5 days.
- Grade 3 or greater febrile neutropenia (temperature $\geq 38.5^{\circ}\text{C}$)
- Grade 4 anemia, unexplained by underlying disease

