4.3 Dose Escalation/De-escalation

If a DLT occurs in 2 or more patients on a dose level during the first cycle, the MTD will be exceeded and we will consider this dose level to be intolerable. If a DLT occurs in 1 of 3 patients during this time, an additional 3 patients will be enrolled at that dose level cohort and evaluated for DLT before dose escalation can proceed. If no other patient in the cohort has a DLT, escalation to the next cohort may proceed 1 week later from the last included patient on the current cohort. If a second patient in a cohort has a DLT, MTD determination will then be conducted by one of the following schemes:

- If ≥ 2 of 3 patients in cohort 1 exhibit a DLT at the dose of 1.5 mg/kg CT-011 in combination with lenalidomide 15 mg, 3 more patients will be enrolled at a de-escalated dose level cohort. This de-escalation cohort (Cohort -1) will use the same dose of CT-011 (1.5 mg/kg) in combination with 10 mg lenalidomide. If no further DLTs are observed, we will consider dose escalation of the CT-011 with this lower dose of lenalidomide such that the dose escalation of CT-011 to 3 mg/kg with lenalidomide 10 mg will proceed in the next cohort. However, if ≥ 2 patients experience DLT with CT-011 1.5 mg/kg and lenalidomide 10 mg, then we will further de-escalate lenalidomide to 5 mg and enroll 3 more patients on CT-011 1.5 mg/kg combined with lenalidomide 5 mg. The same criteria for MTD will be used for these de-escalation dose level cohorts.
- If ≥ 2 patients in cohort 2 exhibit a DLT at the dose of 3 mg/kg CT-011 in combination with lenalidomide 15 mg, we will explore tolerability of an intermediate dose level of lenalidomide, where 3 patients will be enrolled and treated with 3 mg/kg of CT-011 in combination with 10 mg lenalidomide. The dose escalation of CT-011 to 6 mg/kg with lenalidomide 10 mg will proceed in the next cohort if no more than one DLT is observed in the 3 mg/kg CT-011+10mg lenalidomide cohort.
- If ≥ 2 patients in cohort 3 exhibit a DLT at the dose of 3 mg/kg CT-011 in combination with lenalidomide 25 mg, 3 more patients will be enrolled at the 3 mg dose of CT-011 in combination with 15 mg lenalidomide. If there is < 1 DLT with CT011 3mg/kg and lenalidomide 15 mg, this will be defined as the MTD. If there are 2 or more DLT, then 3 additional patients will be enrolled at the CT-011 3mg/kg and lenalidomide 10 mg, which will become the MTD.

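### After a cohort is expanded, the plan lets the next dose level open one week after the last patient is included, although the required DLT evaluation covers the 28-day Cycle 1

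*Combined protocol and SAP*

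**What the plan says.** **The requirement to evaluate.** After a DLT in one of three patients, Section 4.3 states that "an additional 3 patients will be enrolled at that dose level cohort and evaluated for DLT before dose escalation can proceed". The Synopsis (Dosing Regimen) has the same rule: "an additional 3 patients will be enrolled and evaluated for DLT before dose escalation can proceed".

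**The clause.** In both places the next sentence says that, provided a second DLT is not seen at that level, "escalation to the next cohort may proceed 1 week later from the last included patient on the current cohort".

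**The DLT window.** Section 4.2 counts "toxicities considered to be at least possibly related to one of the study drugs during Cycle 1". Section 4.1 sets the cycle length, with "lenalidomide given at 15, 15, 25, and 25 mg orally daily on days 1-21 of a 28-day cycle". The Synopsis (Study Design) adds: "Dose escalation will be determined based on the occurrence of DLTs observed in the first cycle of therapy".

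**Related text.**
- Section 6.1.1 places DLT evaluation of each cohort before the escalation decision.
- Section 4.3 and the Synopsis replace phase I patients who leave before finishing Cycle 1 for reasons other than toxicity or DLT.
- The Synopsis (Dosing Regimen) also asks for "A minimum of 3 patients to a cohort with at least one week break between cohorts", without saying when the break starts.

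**The concern.** The first sentence makes escalation wait for a Cycle 1 evaluation of the added patients. The second permits it one week after the last of them is included. Nothing in the documents says which prevails, or that the week starts when Cycle 1 is complete.

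This rule controls when new patients may receive a higher dose, and it applies exactly where one DLT has already occurred and a second would rule the level out. The next step can be large: lenalidomide 15 to 25 mg between cohorts 2 and 3, or CT-011 3 to 6 mg/kg between cohorts 3 and 4. New patients could be treated at that higher dose before the current level is shown to exceed the MTD.

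**Working it through.** The plan states no figure to reproduce here, so the check has two parts: timing, which comes from the documents, and an illustration of the consequence, which needs assumptions.

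**Timing**

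Inputs: one week from the last included patient (4.3); 28-day cycle with lenalidomide on days 1–21 (4.1); CT-011 on day 3 (5.1.3); treatment to start within 72 hours of registration (7.1).

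| | Inclusion = first dose | Inclusion = registration, first dose 72 h later |
|---|---|---|
| Treatment day one week after inclusion | 8 | 7 − 3 + 1 = 5 |
| Window days left | 28 − 7 = 21 | 28 − 4 = 24 |
| Lenalidomide doses left | days 8–21 = 14 | days 5–21 = 17 |
| Days since the CT-011 infusion | 8 − 3 = 5 | 5 − 3 = 2 |

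One DLT criterion in Section 4.2 is grade 4 neutropenia that lasts longer than 5 days. With onset on day d, it is established by day 8 only if d + 5 < 8, so d ≤ 2. By day 5 it would need d < 0, so it cannot be established.

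Some toxicity data may exist by then. Section 5.8.5 has sampling on days 4 and 6 of Cycle 1, and Section 5.8.2 assesses toxicity at each outpatient visit. These data cannot cover the remaining three weeks.

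**Is the clause harmless if the week is a minimum added to the Cycle 1 evaluation?** A patient who has completed 28 days is already past one week from inclusion. Counted from inclusion, the clause can therefore change the escalation date only by bringing it forward to before Cycle 1 ends.

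**Illustration**

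The documents give neither a DLT rate nor an onset pattern. Let p be the true Cycle 1 DLT rate and f the share of DLTs that have appeared at the one-week look. Uniform onset over 28 days gives f = 7/28 = 0.25.

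- P(escalate) = (1−p)³ + 3p(1−p)² × Q
- Full Cycle 1 for all: Q = (1−p)³
- Only the sixth patient incomplete: Q = (1−p)²(1−fp)
- Chance that the sixth patient has the second DLT after the level was cleared by the clause: (1−f)p / (1−fp)

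At p = 0.33 and f = 0.25, (1−p)³ = 0.301 and 3p(1−p)² = 0.444.
- Full cycle: 0.301 + 0.444 × 0.301 = 0.434.
- Sixth patient incomplete: Q = 0.4489 × 0.9175 = 0.412, and 0.301 + 0.444 × 0.412 = 0.484.
- Later second DLT: 0.2475 / 0.9175 = 0.27.

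| p | f | P(escalate), full cycle | P(escalate), clause | Chance of later second DLT |
|---|---|---|---|---|
| 0.25 | 0.25 | 0.600 | 0.644 | 0.20 |
| 0.33 | 0.25 | 0.434 | 0.484 | 0.27 |
| 0.50 | 0.25 | 0.172 | 0.207 | 0.43 |
| 0.33 | 0.50 (early onset) | 0.434 | 0.467 | 0.20 |
| 0.33 | (7/28)² = 0.0625 (late onset) | 0.434 | 0.496 | 0.32 |

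At f = 0.25 the rises, before rounding of the probabilities, are 4.4, 4.9 and 3.5 percentage points.

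Only the sixth patient is treated as incomplete here. The plan states no stagger within a cohort. If all three added patients started together, Q at p = 0.33 would be (1 − 0.25 × 0.33)³ = 0.772 instead of 0.301, and P(escalate) would be 0.301 + 0.444 × 0.772 = 0.644.

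**The case against.** The strongest defence is that the permission is conditional. It applies only if no other patient in the cohort has a DLT, and since a DLT is defined over Cycle 1, that is known only when Cycle 1 ends. Read in sequence, the text would mean evaluate, confirm that there is no second DLT, then leave a one-week gap such as the break in the Synopsis. The clause also does not name the event that starts the week; if it runs from completed evaluation, it has a real and harmless effect. The Synopsis, Section 4.3 and Section 6.1.1 all point to a full-cycle evaluation.

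Much of this stands as evidence of intent: the authors probably meant a full cycle. It does not remove the defect. The clause ties the week to the last included patient and never mentions completion of evaluation, and no other text does so. A reader can also take the condition to mean that no DLT has been seen so far.

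A second point is that registration is central (7.1, 7.5) and all sites join monthly teleconferences (Appendix E), so a subsite would not open a dose level on its own reading. That stands. The remaining risk is that the coordinating centre applies the clause as written.

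Third, the probabilities are assumed and the rises in the base case are modest. That is correct, and the finding does not depend on them. The day-5 figures also need inclusion to mean registration and the full 72 hours to be used; day 8 needs neither.

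**Conclusion.** The concern holds. Two adjacent sentences, printed in both the Synopsis and Section 4.3, give incompatible earliest dates for escalation after an expanded cohort, and the later sentence is unsafe if followed as written. Given the cycle length, the shortfall is 21 of 28 window days for the last patient, or 24 if inclusion means registration with the full 72-hour lag.

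The effect on escalation is illustrative only. For assumed DLT rates of 25% to 50%, uniform onset and one incomplete patient, the chance of escalating rises by 3.5 to 4.9 points, all of it through the branch with one DLT in the first three patients. In that branch, a level cleared by the clause has a 0.20 to 0.43 chance of a second DLT in the sixth patient.

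The final MTD need not be wrong, because a late DLT still counts: "Any dose level that has two or more DLTs reported is considered to exceed the MTD and not be a tolerable dose level". What is at stake is exposure of new patients to a higher dose before that DLT is known. This should be corrected, because it is a stated dose-escalation rule and not a missing detail.

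**What to change.** Replace the clause in Section 4.3 and in the Synopsis (Dosing Regimen) with: *The next cohort may open only when every evaluable patient in the current cohort has either completed the 28-day Cycle 1 or had a DLT, and the resulting DLT count permits escalation.* In the Synopsis, state that any one-week break between cohorts starts from that point.

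**Cost.** One sentence in two places and one start point.
- Compared with using the clause literally, each affected cohort waits 28 − 7 = 21 days longer, or 31 − 7 = 24 days with the 72-hour lag.
- If the one-week break is kept, that becomes 28 to 31 days.
- If the trial would have waited for Cycle 1 anyway, the replacement sentence adds no time.

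No extra patients or visits are needed, because the checks already planned before Cycle 2 (Section 5.6) can serve as the end-of-window evaluation.

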6.0 STATISTICAL CONSIDERATIONS

6.1 Overview of study design

This is a phase I/II clinical trial designed to first determine the MTD of the combination of CT-011 + lenalidomide in relapsed/refractory MM patients and then to assess the associated efficacy of this regimen in this patient population through evaluation of the overall response rate. The phase I portion follows the standard cohorts-of-3 phase I clinical trial design, and the phase II portion will utilize a one-stage three outcome phase II design (Sargent et al, 2001).

6.1.1 *Phase I portion*

In the phase I portion, we will assess the MTD using a standard cohorts-of-3 phase I trial design, where the MTD is defined as the dose level at which no more than one of 6 patients experiences a dose-limiting toxicity (DLT). The dose escalation rules follow the standard design, where cohorts of 3 are accrued to a dose level and evaluated for DLT before making a decision to dose escalate or not. If in the first 3 patients on a dose level there are no DLTs observed, the next cohort of 3 can be accrued to the next dose level. If one DLT of the first 3 patients at a dose level experiences DLT, then 3 additional patients will be accrued to that dose level to ensure it is tolerable and does not exceed the MTD. Any dose that has two or more patients with DLTs has exceeded the MTD and is deemed to have unacceptable toxicity. If the first dose level proves to have unacceptable toxicity (i.e. 2+ DLTs), then 3-6 patients will be accrued to the de-escalation dose level (dose level -1). For this portion of the trial, we expect a minimum of 12 patients (worst case scenario of 2+ DLTs on dose level cohorts 1, -1, and -2) and a maximum of 30 patients (e.g. 6 at each of the 4 dose levels and an intermediate dose level). Adverse events and toxicities will be summarized using the NCI CTCAE version 4 and based on severity and perceived attribution to study treatment; these outcomes will be assessed and tabulated by dose level.

6.1.2 *Phase II portion*

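### The cohort 2 fallback rule sets a one-DLT threshold with no denominator, so read literally it lets CT-011 double to 6 mg/kg at 1 of 3, against the plan's own expansion rule

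*Combined protocol and SAP*

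**What the plan says.** **General rule.** Section 4.3 states: "If a DLT occurs in 1 of 3 patients during this time, an additional 3 patients will be enrolled at that dose level cohort". The synopsis (Dosing Regimen) says that at 1 of 3 "an additional 3 patients will be enrolled and evaluated for DLT before dose escalation can proceed", and its Study Design text calls for expansion at 1 of 3 without limiting this to the four main cohorts. Section 6.1.1 lets the next level open after three patients only if none had a DLT; with one DLT, "then 3 additional patients will be accrued to that dose level to ensure it is tolerable and does not exceed the MTD". Two or more DLTs mean the level exceeds the MTD.

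**Hand-over to the fallback schemes.** Section 4.3 continues: "If a second patient in a cohort has a DLT, MTD determination will then be conducted by one of the following schemes". Four bullets follow, one per cohort.

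**Cohort 2 bullet.** It opens an intermediate lenalidomide level, "where 3 patients will be enrolled and treated with 3 mg/kg of CT-011 in combination with 10 mg lenalidomide". CT-011 then goes to 6 mg/kg with lenalidomide 10 mg "if no more than one DLT is observed in the 3 mg/kg CT-011+10mg lenalidomide cohort". The synopsis repeats this text.

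**Neighbouring bullets.** In Cohort -1 (the cohort 1 fallback) the condition is stricter: "If no further DLTs are observed, we will consider dose escalation of the CT-011 with this lower dose of lenalidomide". That bullet ends by applying the same MTD criteria to its de-escalation cohorts, and section 6.1.1 allows 3 to 6 patients there. The cohort 3 and cohort 4 bullets act on fewer than one DLT or on two or more, and say nothing about exactly one.

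**Phase I size.** Section 6.1.1 gives "a maximum of 30 patients (e.g. 6 at each of the 4 dose levels and an intermediate dose level".

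**The concern.** The cohort 2 bullet is the specific instruction that the lead-in sends the team to, and it carries its own size and threshold. A specific rule that appears to depart from a general one can be taken as an exception to it. On that reading CT-011 is doubled with a DLT in 1 of 3 patients and none of the three confirmatory patients treated.

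The branch is a sensitive one. Cohorts 1 and 2 share lenalidomide 15 mg and differ only in CT-011 (1.5 against 3 mg/kg). A failure in cohort 2 after cohort 1 has passed may therefore point to the CT-011 increase, although chance could also explain it. The earlier single-agent study found no MTD up to 6 mg/kg (section 1.4.2), which is reassuring but is not evidence on this combination.

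**Working it through.** **The plan's own figure.** Six at each of four levels plus six at an intermediate level: 6 × 4 + 6 = 30. This reproduces the stated maximum, and it shows that an intermediate level was expected to expand to six.

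**The two readings.** Both the general rule and the bullet are satisfied if the cohort is first expanded at 1 of 3 and CT-011 is then escalated at no more than 1 of 6. The readings part only when exactly 1 of the first 3 patients has a DLT.

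**Step 1: within the fallback cohort.** Let p be the true DLT rate there (assumed, since the documents give none).
- With expansion: S(p) = (1−p)³ + 3p(1−p)² × (1−p)³
- Literal, at most 1 of 3: L(p) = (1−p)³ + 3p(1−p)²

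| p | S(p) | L(p) | Difference |
|---|---|---|---|
| 0.10 | 0.906 | 0.972 | 0.066 |
| 0.20 | 0.709 | 0.896 | 0.187 |
| 0.30 | 0.494 | 0.784 | 0.290 |
| 0.40 | 0.309 | 0.648 | 0.339 |
| 0.50 | 0.172 | 0.500 | 0.328 |

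These are conditional on the fallback cohort having opened. They are not trial-level risks.

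**Step 2: from the start of phase I.** Let p1 and p2 be the DLT rates in cohorts 1 and 2, and q the rate in the fallback cohort.
- Disputed case (cohort 1 passes, cohort 2 fails, then exactly 1 of 3): J = S(p1) × [1 − S(p2)] × 3q(1−q)²
- Disputed case in which the skipped expansion would have stopped escalation: J × [1 − (1−q)³]

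Worked example, p1 = 0.10, p2 = q = 0.20: 0.906 × (1 − 0.709) = 0.264; × 0.384 = 0.101; × (1 − 0.512) = 0.050.

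| p1 / p2 | S(p1)[1−S(p2)] | J, q = p2 | with stop | J, q = p1 | with stop |
|---|---|---|---|---|---|
| 0.05 / 0.10 | 0.0914 | 0.022 | 0.006 | 0.012 | 0.002 |
| 0.10 / 0.20 | 0.264 | 0.101 | 0.050 | 0.064 | 0.017 |
| 0.20 / 0.30 | 0.358 | 0.158 | 0.104 | 0.138 | 0.067 |
| 0.30 / 0.50 | 0.409 | 0.153 | 0.134 | 0.180 | 0.119 |
| 0.20 / 0.40 | 0.489 | 0.211 | 0.166 | not run | not run |

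The q = p1 columns allow for the lower lenalidomide dose making the fallback level as tolerable as cohort 1. For its assumed rates, each figure is a ceiling, because it takes the literal reading as certain to be followed.

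**Step 3: patient numbers with expansion applied.**
- Cohort 2 path (cohorts 1 and 2, 3 mg/kg + 10 mg, 6 mg/kg + 10 mg): 6 × 4 = 24.
- Cohort 3 path: 6 × 3 + 6 + 6 = 30.
- Cohort 4 path: 6 × 4 + 6 = 30 if the first fallback level expands and passes. If it expands and fails, 6 × 4 + 6 + 3 = 33, or 6 × 4 + 6 + 6 = 36 if the second fallback level also expands.

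**The case against.** The strongest reply is that nothing conflicts. The general rule appears in several places, and the synopsis states it for any cohort. The section 4.3 lead-in already uses the word cohort to include expansion patients. Escalating at 1 of 3 means setting all of this aside. This stands as evidence of intent: a reader might infer that the plan deliberately allows or requires escalation at 1 of 3 in this branch, and the documents do not support that. It does not make the bullet clear, because the bullet is the operative instruction there and, unlike the cohort 1 bullet, has no sentence carrying the general criteria over.

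A second reply is that the consequence is contained. Registration is central (section 7.1), so a subsite could not open a dose level alone. Monthly teleconferences and quarterly safety committee review apply (Appendix E). The MTD definition of at most 1 of 6 is untouched, and the next cohort would still stop at two DLTs. All of this stands and limits the severity.

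A reader might also extend the criticism to Cohort -1. That does not hold: the same-criteria sentence and the 3 to 6 patient range in section 6.1.1 cover it.

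Finally, a blanket instruction to expand every fallback cohort would cause trouble. The cohort 3 fallback (3 mg/kg + 15 mg) is cohort 2's own dose. If cohort 2 passed at 1 of 6 and 1 of 3 new patients has a DLT, that dose already has two DLTs and exceeds the MTD under the synopsis and section 6.1.1. This objection is right, and the fix has to allow for it.

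**Conclusion.** The point holds as a minor-to-moderate safety wording error in a contingency branch. Followed literally, the cohort 2 bullet gives a laxer escalation rule than the one the plan states elsewhere and evidently intends. Across the assumed scenarios the disputed case has probability 0.01 to 0.21, and the case in which the expansion would have stopped escalation has probability 0.002 to 0.17. Every one of these rests on assumed DLT rates and on the literal reading being adopted. The gap at exactly one DLT in the cohort 3 and cohort 4 bullets is a smaller defect of the same kind, which the general rule can fill.

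**What to change.** **Main change, in section 4.3 and the synopsis.** Replace the cohort 2 fallback condition with: *if 0 of 3 patients or, after expansion to six, no more than 1 of 6 patients have a DLT in the 3 mg/kg CT-011 + 10 mg lenalidomide cohort*. The cost is one reworded condition in two places and up to three more patients than the literal reading would use. The path stays within the maximum of 30.

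**Secondary clean-up, in the same two places.**
- Cohort 3 and cohort 4 fallbacks: state that exactly 1 of 3 triggers expansion to six.
- Cohort 3 fallback: state that DLTs among the earlier cohort 2 patients at this dose count towards the two-DLT limit. Expansion at 1 of 3 then applies only where cohort 2 had no DLT.
- Cohort 4 fallback: note that the total could reach 33 to 36 if the first fallback level expands and fails. The stated maximum would need raising for that path only.

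Cohort -1 needs no change.
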